### **3.4.2 Inconsistent data**

In general, discrepant data shall be queried and resolved. Handling of inconsistent data and rules for self-evident corrections are specified in the Data Handling Manual.

### **3.4.3 Dates**

Dates will be collected in a day/month/year format. It is possible that the full date is not always available. If the day is missing, the missing day shall be imputed as the 1st of the month. If the month is missing, the missing month shall be imputed as January. If the imputed date lies before the date of the first procedure, than the new date will be calculated as *hospital discharge date after the first procedure +1*.

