4.5 Safety Evaluation

Safety will be evaluated by collection of AEs and SAEs from entry into the study through the 12 months follow-up visit, or until the subject has terminated participation in the study. All adverse events will be followed until they are adequately resolved or stabilized or for 1 month following study completion or termination, whichever comes first.

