4.7.3 Pharmacological Treatment

As recommended by the GOLD guidelines, each subject will continue maintenance bronchodilator therapy, which will include an inhaled long-acting beta agonist, inhaled anticholinergic, or both. These drugs may also be combined with theophylline and/or inhaled corticosteroids at the discretion of the treating physician. The physician will be allowed to adjust the subject's pharmacological regimen as needed during the course of the study to deal with variations in the subject's condition (e.g., COPD exacerbations). However, the subject's medical regimen should be optimized at the pre-Treatment Visit, prior to completing the baseline Six Minute Walk Test and pulmonary function tests. Medically necessary changes in medications or dosages will be recorded in the CRF. Supplemental oxygen utilization should be recorded and monitored throughout the Study.

All subjects enrolled in the study must have current influenza and pneumococcus vaccinations consistent with local recommendations and/or policy.

Prophylactic anti-inflammatory treatment with steroids 50mg/day shall be given 1 day prior, during and after each treatment for up to 15 days. Prophylactic treatment with antibiotics can be considered for at least 5 days if some bleeding occurs during the implantation and there are infiltrations on chest x-ray post Tx or patient has an excess secretion or sputum culture shows pathologic concentration. Pseudomonades effective antibiotics are needed only in case of positive culture in sputum.

Table 3. Visit Schedule

Procedure / Assessment	Visit 1 Baseline Screening (at least 7 days prior to Tx1)	Tx1 RePneu Placement	Visit 2 1 month post Tx1	Tx2 RePneu Placement (4-8 weeks post Tx1)	Visit 3 1 month post Tx2	Optional Tx3 RePneu Placement (4-8 weeks post Tx2)	Visit 3 4 months post final Tx	Visit 4 12 months post Tx1
Informed Consent	X							
Inclusion/ Exclusion	X							
Focused physical exam including vital Signs and SpO ₂	X	X	X	X	X	X	X	X
Spirometry	X						X	X
Lung volumes	X						X	X
6MWT	X						X	X
SGRQ	X						X	X
mMRC	X						X	X
Concomitant medication / O ₂ Use	X	X	X	X	X	X	X	X
Pregnancy testing	X	X		X		X		
Physical activity and energy expenditure for 6-8 days	X						X	X
Bronchoscopic still images			X		X		X	
Static and dynamic pulmonary compliance prior and post Tx			X		X		X	
Echocardiogram	X						X	X
Body composition	X						X	X
V/P SPECT or Lung perfusion scintigraphy	X							X
High Resolution CT	X							X
Chest X-Ray	X	X		X		X		

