7.5 Process for Assessment, Recording and Reporting of AEs

Subjects will be instructed at the beginning of the study to report to the investigator any adverse physical or mental changes they experience and they will be asked about adverse events at each visit, including those experienced at the baseline visit prior to, during, or immediately following treatment, as assigned. All such adverse events reported by the subjects or observed by the investigators will be reported to the Sponsor.

As described in Section 7.0, if the event is deemed to be Serious, such events will be reported to the Sponsor via the completion of the Adverse Event CRF. The Ethics Committee(s) will be informed if the Serious or unexpected adverse event, in the opinion of the Investigator, or the Medical

Monitor, is likely to affect the safety of the subjects or the conduct of the study.

8 Administrative

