## 5.4 Procedural analyses

For the following sections tables will be created to describe the RePneu® procedures.

Additionally a listing will be prepared to show

- the coils per procedure,
- the total coils implanted,
- the total bronchoscopy time and the total fluoroscopy time,
- the post-procedural hospital stays and
- the type of medication prescribed in preparation for the procedure as well as the corresponding name of the medication, the medication start and stop date and the total daily dosage (will only be done for final analyses)

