## 5.5 Safety analyses

A listing for adverse events will be provided for the final analyses, consisting of the following information of each AE:

- Site
- Subject ID
- AE Term
- SOC
- PT
- AE start date
- AE stop date
- Duration of AE
- Procedure dates
- Days post procedures
- Seriousness, including the primary reason for classification as serious
- Relation to device
- Relation to procedure
- Event outcome

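### SAP 3.4.3 gives one rule for all partial dates: a listed stop can precede its start, a post-Tx2 event can fall before Tx2, and pre-Tx1 items always move past discharge (minor)

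*SAP*

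**What the plan says.** SAP 3.4.3 has one rule for all dates. "If the day is missing, the missing day shall be imputed as the 1st of the month"; a missing month becomes January. Then: "If the imputed date lies before the date of the first procedure, than the new date will be calculated as" first-procedure discharge plus one (unit not stated; taken here as days). The rule names no variable type, does not require a stop to be on or after its start, does not check Tx2 or Tx3, and is silent when the year is missing.

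The dates feed two listings. The adverse event listing in SAP 5.5 shows start, stop, procedure dates, "Duration of AE" and "Days post procedures". The procedural listing in SAP 5.4 shows, for preparation medication, "the medication start and stop date and the total daily dosage".

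Items before Tx1 are in scope. Protocol 4.5 provides for "collection of AEs and SAEs from entry into the study through the 12 months follow-up visit", Protocol 7.5 covers events "including those experienced at the baseline visit prior to, during, or immediately following treatment", and Protocol 4.7.3 says of prophylactic steroids that they "shall be given 1 day prior, during and after each treatment for up to 15 days". Protocol Table 3 places screening at least 7 days before Tx1.

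SAP 3.4.1 says that analyses use observed data and impute nothing. SAP 3.4.2 sends discrepant data to queries and to a Data Handling Manual that is not among the documents.

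**The concern.** The earliest possible day is a usual choice for a start date. For a stop date it errs in the wrong direction, because the 1st of the month precedes any start later in that month. The replacement by discharge plus one does two different jobs. It keeps uncertain onsets on the post-procedure side of Tx1, which is cautious, but it also relabels items known to belong before Tx1.

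The study has one arm and stopped early with few patients. The adverse event tables in SAP 5.5.1 to 5.5.3 are counts by SOC and PT with no time window, so the listing is where a reader sees how an event sits in time against each procedure. A screening event shown after discharge, or a post-Tx2 event shown before Tx2, would mislead on that point.

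**Working it through.** The documents give no figure to reproduce, so the rule was applied literally and enumerated over every day of a 365-day year, with the day missing and the month and year known. The spread of durations, the length of stay and the calendar dates are assumptions. The 4-8 week gap between Tx1 and Tx2 is from Protocol Table 3.

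**1. Stop before a known start, discharge replacement not triggered.** The stop becomes the 1st of its month. It precedes the start whenever start and stop share a month and the start is not on the 1st.
- Durations 0-7 days: a month of L days gives 8L - 36 such pairs out of 8L. Over the year: 8 × 365 - 12 × 36 = 2,488 of 2,920 = 85.2%.
- Durations 0-14 days: 15 × 365 - 12 × 120 = 4,035 of 5,475 = 73.7%.
- Durations 0-30 days: the sum of L(L - 1)/2 is 7 × 465 + 4 × 435 + 378 = 5,373 of 11,315 = 47.5%.

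For stays of 1 or 3 days these figures hold for starts on days 8-30 after Tx1. For a 7-day stay they are 82.6%, 71.6% and 46.4%.

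**2. The same, for starts on days 0-7 after Tx1, replacement included.**

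| Assumed stay | Durations 0-7 | 0-14 | 0-30 |
|---|---|---|---|
| 1 day | 54.5% | 47.3% | 30.8% |
| 3 days | 36.1% | 31.7% | 21.6% |
| 7 days | 11.5% | 11.5% | 10.2% |

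The replacement lowers the share but does not remove the fault.

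**3. Events on days 0-7 after Tx2.** With gaps of 28-56 days and the replacement included, 85.2% are dated before Tx2. The count is as in step 1: the 1st of the month precedes Tx2 unless the event falls in a later month or Tx2 is on the 1st. Where the replacement applies, the day after Tx1 discharge is still before Tx2.

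**4. Items that truly precede Tx1.** The imputed date is never later than the true date. A true date before Tx1 therefore always meets the trigger. Enumerated for 1-30 days before Tx1: 365 × 30 = 10,950 of 10,950 moved past discharge.

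**5. What removing the replacement altogether would do.** For starts on days 0-7 after Tx1, the 1st of the month precedes Tx1 in 2,488 of 2,920 = 85.2%, against none under the present rule.

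**6. Example** (assumed Tx1 14 March, discharge 17 March, Tx2 20 April).
- Start 10 May, stop recorded as May: stop 1 May, duration -9 days.
- Event on 21 April recorded as April: 1 April, 19 days before Tx2.
- Preparation medication begun 13 March recorded as March: 1 March precedes Tx1, so 18 March, four days after Tx1.

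**The case against.** The strongest reply is that this touches a few cells in per-patient listings, perhaps none. Partial dates may not occur. Protocol 10 requires full source verification of safety data, Protocol 7.1 has SAEs reported within two working days, SAP 2.2 provides a monthly safety listing, and SAP 3.4.2 has discrepancies queried. Procedure dates stand in the same row as the event dates, so an inverted pair would be visible. Duration is recorded on the CRF under Protocol 7, SAP 5.5 gives no formula for it, and the SAP does not say whether listings show dates as collected or as imputed. All of this stands, and it is why the point is minor. It does not make the rule correct: SAP 3.4.3 governs whatever stays partial after those checks, and the footnotes in SAP 3.5 can disclose a derivation but not repair it.

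The discharge replacement also has a sound purpose, since it assigns an onset of uncertain order to the post-procedure side. A reader might infer that it should simply be deleted. Step 5 shows why not: that would create at Tx1 the fault that now exists at Tx2.

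A reader might also infer that adverse event counts or device-relatedness are distorted. The documents do not support that. The tables in SAP 5.5.1 to 5.5.3 use no dates, relatedness is recorded rather than derived from timing, and the 6MWD analysis does not use this rule.

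**Conclusion.** The rule is wrong as written, and the point is minor. For partial dates with a known year, a stop before its start and a post-Tx2 event dated before Tx2 can occur; the move of a true pre-Tx1 item past discharge is certain, by logic. The reach is limited to dates, "Days post procedures", and "Duration of AE" if it is derived from dates, in the SAP 5.4 and 5.5 listings.

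The percentages are conditional on a missing day and on uniform calendar dates and durations, and those for starts near Tx1 also depend on the assumed stay. They are not estimates of how many records are wrong; that number is unknown and may be zero. SAP 3.4.1 and 3.4.3 also need reconciling, because one rules out imputation and the other imputes dates.

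**What to change.** Replace the single rule in SAP 3.4.3 with the following.

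- (a) Partial stop date: last day of the known period, capped at death or study exit (including the one-month adverse event follow-up in Protocol 4.5), and never before the start date.
- (b) Partial start date: first day of the known period, never after a known stop date.
- (c) Do not apply discharge plus one when the known period lies wholly before Tx1, when a known stop precedes Tx1, or when the record is a screening event or preparation medication. Keep a post-procedure assignment for other adverse event starts whose known period contains Tx1, never after a known stop date.
- (d) Show the partial date as collected, flag the imputed value, and list "Days post procedures" as undetermined where the known period contains a procedure and the order cannot be established.
- (e) State that the date rule is for listings only, which reconciles it with SAP 3.4.1.

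The cost is SAP wording and a few lines of code, with no new data. There are two downsides. Some timing fields become undetermined: about 85% of day-missing events on days 0-7 after a procedure (2,488 of 2,920, treating a procedure on the 1st as determinable). A month-end stop overstates duration by 5,373/365 = 14.7 days on average, as much as the 1st-of-month stop understates it where the replacement is not triggered. An imputed start near Tx2 also remains the 1st of the month. For both reasons the flag is needed.

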## **3.5 Derived Datasets, Variables and Terms**

Derivations will be specified in a footnote where feasible.

The Body Mass Index (BMI) will be calculated as  
 $BMI = \text{weight in kg} / \text{height in m}^2$ .

Change from Baseline will be calculated as  
 $\text{mean}(\text{parameter})[\text{time slot}] - \text{mean}(\text{parameter})[\text{baseline}]$ .

Percentage change from Baseline will be calculated as  
 $\text{mean}(\text{parameter})[\text{time slot}] - \text{parameter}[\text{baseline}] / \text{parameter}[\text{baseline}] * 100$

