#### 3.3.1 Descriptive statistics

Continuous variables will be displayed including arithmetic mean, standard deviation (SD), minimum (min), median and maximum (max). Additionally, the number of patients in the analysis set (ITT), those contributing to the analysis (N) and the number of patients not included in the analysis due to missing data (missing) will be displayed.

The Change from Baseline will be calculated for each patient individually and averaged for values at baseline (mean, SD, min, median, max at baseline), values at each visit (mean, SD, min, median, max at visit) and the change from baseline to each visit.

Categorical variables will be displayed as frequencies and percentages (i.e. absolute and relative frequencies). If not specified otherwise, the percentages will be based on all patients respectively procedures available for analysis (non-missing and missing). The number of patients with missing data will also be summarized.

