### **3.3.2 Effectiveness and Safety Analyses**

The endpoints will be analyzed with a paired t-test, which will compare baseline to 3-month post final treatment and 12-months post first treatment follow-up values. A p-value of <0.05 will be considered statistically significant. Adverse events will be categorized into medically relevant categories and presented as frequency counts and percentages. All results tables and plots shall clearly display the total number of patients in the analysis set (N) and the number of patients with evaluable data (n).

Output designs or minor changes in the tables may be adapted to programming and/or sponsor demands.

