### **5.3.3 Baseline Characteristics**

A table showing the following baseline characteristics will be presented for the final analyses:

- FVC in L (continuous)
- FVC % predicted (continuous)
- FEV1 in L (continuous)
- FEV1 % predicted (continuous)
- (FEV1 in L/FVC in L) in % (continuous)
- RV in L (continuous)
- RV % predicted (continuous)
- 6MWT in m (continuous)
- mMRC (0, 1, 2, 3, 4) (categorical)
- mMRC (continuous)

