## **5.6 Effectiveness analyses**

The following summary listing of effectiveness parameters will be produced for the final analyses showing the following parameters at baseline, at assessed visits, change from baseline to assessed visits and, for some variables, if the MID was reached for (Responder):

- 6MWT in m over time (Responder:  $\geq 25m$ )
- Forced expiratory volume in one second (FEV1) (Responder:  $\geq 10\%$ )
- Residual volume (RV)
- Residual volume/total lung capacity (RV/TLC)
- Diffusion capacity (DLCO)
- mMRC dyspnea scale
- Heart rate
- Body composition including BMI

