### **5.6.1 Primary effectiveness endpoint**

Changes at 3 months post final treatment and 12 months post first treatment in:

- Minute Walk Distance (6MWD)

The change from baseline as continuous variable and the responder analysis as categorical variable will be presented.

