### **5.6.2 Secondary effectiveness endpoints**

Due to the small sample size, the secondary effectiveness endpoints will only be listed. The assessments and change from baseline will be presented per patient in the efficacy listing.

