## APPENDIX I: OVERVIEW OF TABLES, FIGURES AND LISTINGS TO BE PRODUCED

### Overview of planned tables

Programmer Note: Please adapt the numbering of subgroup tables as may be necessary.

Table Number	Title	Analysis Set for Final Analyses	Subgroup Analyses 
14.1.1	Patient accountability	ITT	No
14.1.2	Study terminations	ITT	No
14.2.1	Enrollment by site	ITT	No
14.2.2	Demographics	ITT	No
14.2.3	Baseline characteristics	ITT	No
14.2.4	Medical history	ITT	No
14.2.5	History and characterization of emphysema	ITT	No
14.2.6	Treatment of emphysema	ITT	No
14.3.1	Number of devices implanted	ITT	No
14.3.2	Procedure time	ITT	No
14.3.3	Post-procedure hospital stay	ITT	No
14.6.1	Adverse events	ITT	No
14.6.2	Serious adverse events	ITT	No
14.6.3	Device and procedure related adverse events	ITT	No
14.7.1	Change from baseline in 6MWT in m	ITT	No
14.7.2	Number and percentage of patients achieving change in 6MWT in m $\geq 25$	ITT	No

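### SAP 3.5's percent-change formula is wrong as printed, its use of mean() is undefined, and the FEV1 10% responder flag does not say relative change or percentage points

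*SAP*

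**What the plan says.** SAP 3.5 gives two derivation lines. Writing V for the parameter at a time slot and B for the parameter at baseline, they are:

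- change: mean(V) − mean(B)
- percent change, introduced by "Percentage change from Baseline will be calculated as": mean(V) − B / B * 100

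The second line has no brackets around the difference and applies mean() to the visit term only. Section 3.5 does not say what mean() averages over. It promises footnotes for derivations where that is practicable, without giving their content. Neither document contains another percent-change formula.

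Elsewhere the SAP works patient by patient:

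- Section 3.3.1: "The Change from Baseline will be calculated for each patient individually", with mean, SD, minimum, median and maximum of the change to follow.
- Section 3.3.2: "The endpoints will be analyzed with a paired t-test, which will compare baseline to 3-month post final treatment", and likewise at 12 months.
- Section 5.6.1, for 6MWD: "The change from baseline as continuous variable and the responder analysis as categorical variable will be presented".
- Section 5.6.2, for secondary endpoints: "The assessments and change from baseline will be presented per patient in the efficacy listing".
- Appendix I: Table 14.7.1, "Change from baseline in 6MWT in m", and Table 14.7.2, which counts patients who gain at least 25 m.

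Section 5.6 has the entry "Forced expiratory volume in one second (FEV1) (Responder", followed by a threshold of 10% or more. It refers to no derivation. Section 5.3.3 tabulates baseline FEV1 both in litres and as % predicted.

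**The concern.** Section 3.5 is where a programmer looks for derivations, and it raises three questions.

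1. By the usual order of operations, the percent-change line does not compute a percent change.
2. The change line can be read as a difference of two group means. Such a quantity has no SD, median or range, and gives no value for a single patient. The summaries in 3.3.1, the paired t-test and the listing need exactly those.
3. The FEV1 flag is the one output that appears to need a percent change, yet 5.6 does not tie it to 3.5. Nor does it say whether 10% is relative to the patient's baseline or is 10 points on the % predicted scale.

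What is at stake is which patients are marked as FEV1 responders and, on one reading only, the mean change shown for 6MWD.

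**Working it through.** **Inputs.** The two lines in SAP 3.5; the 10% threshold in SAP 5.6; entry at FEV1 no higher than 45% predicted (inclusion criterion 3 in both documents); historical mean FEV1 gains of +0.06, +0.07 and +0.11 L (Protocol 2.3, Table 1). The documents give no baseline FEV1 in litres, so 0.70 L is an assumption. The 6MWD values in step 3 are also assumed. The plan states no result here that could be reproduced.

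**Step 1: the percent-change line as printed.** B / B * 100 = 100 for any non-zero baseline, so the result is V − 100.

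| Assumed FEV1 | As printed | (V − B)/B × 100 |
|---|---|---|
| 0.70 to 0.76 L | 0.76 − 100 = −99.24 | 0.06/0.70 = +8.6% |
| 0.70 to 0.77 L | 0.77 − 100 = −99.23 | 0.07/0.70 = +10.0% |
| 0.70 to 0.81 L | 0.81 − 100 = −99.19 | 0.11/0.70 = +15.7% |

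A printed result of 10 or more needs V of at least 110. That is impossible in litres. On the % predicted scale, a patient who enters at 45% would have to gain 110 − 45 = 65 points.

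**Step 2: the one-sided mean().** If mean(V) is the patient's own value in that time slot, brackets alone repair the line. If it is a group mean, the bracketed line still compares the group's visit mean with one patient's baseline, and is not a per-patient percent change.

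**Step 3: the change line, if mean() is a group mean.** Take assumed 6MWD baselines of 250, 300, 350 and 400 m (mean 325) and visit values of 300, 340, 380 and 420 m (mean 360).

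- Complete pairs: paired changes are 50, 40, 30 and 20, mean 35 m. The difference of means is 360 − 325 = 35 m. They agree.
- Last two follow-ups missing, all baselines kept: the paired mean is (50 + 40)/2 = 45 m. The difference of means is 320 − 325 = −5 m.
- First baseline missing, all follow-ups kept: the paired mean is (40 + 30 + 20)/3 = 30 m. The difference of means is 360 − 350 = 10 m.

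So a gap on either side separates the two definitions once unpaired values are kept. SAP 3.4.1 uses observed data without imputation, so such gaps would remain.

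**Step 4: relative change against percentage points.** With the predicted value held constant, a relative change r from a baseline of p% predicted is r × p points.

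- At the 45% limit: 10% relative = 0.10 × 45 = 4.5 points, and 10 points = 10/45 = 22.2% relative.
- At an assumed 20%: 10% relative = 2.0 points, and 10 points = 10/20 = 50% relative.

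A patient who enters at 45% and improves by between 10% and 22.2% is a responder on the relative reading and a non-responder on the points reading. At lower baselines that band is wider.

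**The case against.** The strongest reply is that this is a notation slip with an obvious correction. A line labelled as percentage change would hardly be coded as V − 100, and brackets may have been dropped when the PDF was read. The inline slash and asterisk make that less likely but do not exclude it. SAP 3.3.1, 3.3.2 and 5.6.2 already fix the per-patient reading of change. The deaths listing in 5.5.4 uses time slot as a per-subject field, so mean(V) may simply be one patient's value in a visit window. The effectiveness listing shows each patient's baseline, visit value and change, so anyone can recompute the flag and an absurd result would be noticed.

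Most of this stands, and it limits the size of the point. It does not remove it. The text as printed is still wrong, 3.5 does not define mean(), and no section settles relative change against points. Protocol Table 1 heads its FEV1 columns with both % and L, so the historical data do not settle it either.

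Three stronger readings are tempting:

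- A reader might infer that 3.5 flatly contradicts 3.3.1 and that the primary analysis is compromised. The inconsistency exists only if mean() is a group mean. A paired t-test uses individual differences by construction, and the 25 m rule is an absolute gain per patient.
- A reader might infer that no patient will be flagged as an FEV1 responder. Section 5.6 does not say that the flag uses 3.5, and the intended formula is easy to guess.
- A reader might infer that the plan must also choose between litres and % predicted. Once the flag is a relative change, both give the same answer if the predicted value is constant.

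**Conclusion.** The point holds as a minor defect of specification. As printed, the percent-change formula equals the visit value minus 100 and has mean() on one term only. The change line is inconsistent with 3.3.1 only on the group-mean reading. The FEV1 flag leaves open relative change or percentage points, and that choice alters who counts as a responder.

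The consequences are small. The FEV1 flag is a secondary output shown only in Listing 16.6; SAP 4 and 5.6.2 rule out tables for secondary endpoints. For 6MWD, the t-test and Table 14.7.2 are unaffected. Only the mean in Table 14.7.1 could move, and only if group means were taken over unpaired values.

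This rests on the formula having been read correctly from the PDF, on the assumed baselines and walk distances used for illustration, and on a constant predicted FEV1 in the scale comparison. If brackets were in fact printed, the V − 100 result falls away. The undefined mean() and the open scale of the flag remain.

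**What to change.** In SAP 3.5 replace both lines with per-patient definitions, for patients with both values:

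- change_i = visit_i − baseline_i
- percent change_i = 100 × (visit_i − baseline_i) / baseline_i

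In SAP 5.6 add one sentence stating that the FEV1 flag of 10% or more uses this per-patient relative change. If percentage points of % predicted were intended, say that instead.

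The cost is two formula lines and one sentence. It needs no new data, table or listing.
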